1.4 Preliminary Data

There has no comparison of the data collected at this time

1.5 Sample Size Justification

For investigation of improved onset time of analgesia, a smaller sample of 34 subjects in each group (N1=34, N2=34) will be sufficient to maintain 80% power and 0.05 alpha level of statistical significance to show 35% decrease in onset time from 20 min to 13 min (effect 0.7) to achieve the Supraclavicular Block with combined use of ultrasound and nerve stimulator.

According to classic studies Williams et al 2003 (doi: 10.1213/01.ANE.0000086730.09173.CA), onset of sensory block parallels onset of partial motor blockade and was 14+/-6 vs 18+/-6 min for ultrasound-guided vs nerve-stimulator guided supraclavicular block.

This was calculated using the power calculation for sample size for continuous outcomes as the dependent variable and two independent samples for the independent variable.

Accrual rates should be about 50% of the available upper extremity renal transplant / vascular graft procedures which should happen at a rate of 2-4 per week.

However, for observation of qualitative data, we decided on a sample size of 100 (N1=50, N2=50).

1.6 Study Variables

A. Independent Variables, Interventions, or Predictor Variables

The only difference (the intervention) between the study groups involves the use of the nerve monitor during the performance of the block

The performance of the block with both the ultrasound and the nerve monitor is in excess of the standard of care which utilizes the ultrasound alone , but the needle used for the block is the same in both groups. It is the Stimuplex Teflon coated needle which can be used with or without application of the nerve monitor function

B. Dependent Variables or Outcome Measures

I have expectations that the use of the nerve block monitor will result in a faster speed of onset of the block as the performance characteristics of the block placement relative to the target nerve may be improved.

Dependent variable would be success of the block as measured objectively by speed of onset.

1.7 Drugs/Devices/Biologics

N/A

1.8 Primary Specimen Collection

N/A

1.9 Interviews, Focus Groups, or Surveys

N/A

1.10 Timetable/Schedule of Events

The data collection will take less than 30 min. per patient.

We anticipate it will take two years to accrue 100 participants and complete the study recruitment.

2.0 Project Management

2.1 Research Staff and Qualifications

All investigators will provide documentation of completing CITI training for research on human subjects.

All licensed physicians involved with the study will be competent in the administration of ultrasound-guided supraclavicular blocks under the guidance of the attending anesthesiologist.

All investigators are staff MD in the anesthesia department accustomed to the performance of the supraclavicular block

2.2 Resources Available

All staff have reviewed the protocol and their functions in the study

2.3 Research Sites

The research will be conducted in the RWJ Barnabas facility

3.0 Multi-Site Research Communication & Coordination

N/A

3.1 Outside Research

N/A

4.0 Research Data Source/s

4.1 Primary Data-Subjects and Specimens

N/A

4.2 Subject Selection and Enrollment Considerations

A. Recruitment Details

Recruitment will entail a discussion about the study including, but not limited to, description and purpose of the study, and risks and costs to the patient. Patient will be given ample time to make a decision for their consent.

Patients will be recruited during their visit at the Pre-Admission Clinic or at the Holding Area prior to entering the Operating Room.

For patients sent to the Pre-Admission Clinic by their Surgeon, they are seen at least 48 hours before their scheduled day of surgery. During this time, recruitment is discussed. These patients will have at least 48 hours to contemplate their decision. Prior to entering the Operating Room, their consent will be finalized at the Holding Area.

For patients who arrive from their home, including those scheduled to go home or stay in the hospital after surgery; they arrive at the Holding Area at least 1.5 hours prior to their surgery. During this time, patients will be recruited and given at least 30 minutes to contemplate their decision and finalize consent.

For patients who are already in the hospital and are scheduled for surgery, they arrive at the Holding Area at least 1 hour prior to their surgery. Like the patients who arrive from home, they are given at least 30 minutes to contemplate their decision and finalize consent.

B. Source of Subjects

Patients will be recruited during their visit at the Pre-Admission Clinic or at the Holding Area prior to entering the Operating Room.

For patients sent to the Pre-Admission Clinic by their Surgeon, they are seen at least 48 hours before their scheduled day of surgery. During this time, recruitment is discussed. These patients will have at least 48 hours to contemplate their decision. Prior to entering the Operating Room, their consent will be finalized at the Holding Area.

For patients who arrive from their home, including those scheduled to go home or stay in the hospital after surgery; they arrive at the Holding Area at least 1.5 hours prior to their surgery. During this time, patients will be recruited and given at least 30 minutes to contemplate their decision and finalize consent.

For patients who are already in the hospital and are scheduled for surgery, they arrive at the Holding Area at least 1 hour prior to their surgery. Like the patients who arrive from home, they are given at least 30 minutes to contemplate their decision and finalize consent.

C. Method to Identify Potential Subjects

Potential subjects are patients who are scheduled for elective upper arm surgery, who will undergo ultrasound-guided supraclavicular block between the ages of 21 and 89, and are not excluded by the exclusion criteria.

D. Subject Screening

Patients will be told about the research study: its description, objectives, risks and benefits, its cost to the patient, and the patient's right to change their mind at any time. This will be done by an RWJUH anesthesiologist or anesthesiology resident at the Pre-Admission Clinic or Holding Area.

▪ Inclusion Criteria

All patients scheduled for elective upper arm surgery with ultrasound-guided supraclavicular block between the ages of 21 and 89 years are eligible to participate if they are able to consent to the study and the performance of the supraclavicular block.

These patients will most likely have chronic renal disease requiring creation / repair of AV fistula / grafts. However, other patient populations can be recruited as well if they meet inclusion criteria, and these characteristics should not affect relevancy of the outcome variables for the supraclavicular block.

▪ Exclusion Criteria

The following patients are excluded from this study:

1. Patients unable to communicate in English
2. Pregnant women
3. Persons with allergies to local anesthetics
4. Persons with infection at or near site of needle insertion
5. Patients with severe disturbance of cardiac rhythm and heart block
6. Patients with severe respiratory compromise
7. Patients requiring bilateral upper extremity anesthesia
8. Patients with coagulopathy or medical anticoagulation
9. Patients with traumatic nerve injury to neck or upper extremity
10. Patients with preexisting neurological deficits in the distribution of the block
11. Patients with previous surgery to the neck that may distort brachial plexus anatomy.

Exclusion criteria include contraindications or relative contraindications to supraclavicular blockade.

Pregnancy is excluded because of high neonatal blood levels of amide local anesthetics due to placental transfer and impaired elimination with possible fetal bradycardia and acidosis.

The drug under study is known to cause birth defects in some animals. It is likely that it may also cause birth defects in people. For this reason, no one can be in this study who is pregnant or who could get pregnant while taking the study drug. Any woman of childbearing age and are sexually active, are asked about the possibility of being pregnant, and may be asked to give a urine sample for a pregnancy test prior to the procedure and the surgery.

The pediatric population is excluded because children are unlikely to understand the study design, give informed consent/assent, and be cooperative during performance of regional anesthesia.

Patients should not take any over-the-counter medicines, herbal products, vitamins or food supplements while taking part in this study, unless they tell the study doctor and get permission from the study doctor to go on taking these medicines.

E. Recruitment Materials

N/A

F. Lead Site Recruitment Methods

N/A

4.3 Subject Randomization

Subjects will be randomized into 2 treatment groups. The experimental group (n=50) will receive an ultrasound guided supraclavicular block performed with a nerve stimulator. The control group (n=50) will receive the standard treatment for an ultrasound guided supraclavicular block).

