1.3 Research Design and Methods

A. Order of occurrence of research procedures

The research procedure involves use of the nerve stimulator technology of the blockade monitor

The study is designed to compare the effectiveness of using a nerve stimulator in conjunction with ultrasound guidance when performing a supraclavicular block. Nerve stimulators have been used for

many years in the performance of various peripheral nerve blocks. With the advent of ultrasound technology, a majority of practitioners have abandoned the use of nerve stimulators and perform these blocks with the ultrasound as the only method of confirming needle location. There have not been many studies to compare the onset, quality, or duration of ultrasound guided supraclavicular blocks with or without the use of a nerve stimulator.

We propose a randomized study design, based on two groups (standard and test treatments). All patients between the ages of 21 and 89 that can communicate in English and meet the selection criteria that are scheduled for upper extremity surgery are eligible to participate.

After consenting to the study, the patient will be randomly assigned to one of two groups, standard or test treatment.

Patients in both groups will receive:

- IV placement on the non-surgical arm with IV fluid infused at 1 ml/kg/hr
- Oxygen by nasal cannula
- Sedation with Midazolam
- Oximetry and EKG monitoring
- Ultrasound-guided supraclavicular block performed as follows:
 - After adequate IV sedation, chloroprep antiseptic solution will be applied to sterilize the injection site.
 - The Sonosite ultrasound probe will be placed in a sterile wrapping and used to identify the subclavian artery as it transverses the upper thorax in the fascia superior to the apex of the lung.
 - The skin overlying the superior aspect of the ultrasound-identified site will be anesthetized with 1% Lidocaine.
 - Through the anesthetized area, a Braun 4 x 21 Stimuplex needle (#4894260) will be inserted and using ultrasound guidance, directed to the area surrounding the subclavian artery.
- In the Standard Group, in the absence of paresthesia and after negative aspiration, the 40 ml of local anesthetic block will be administered.

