4.5 Number of Subjects

A. Total Number of Subjects

Locally, we shall aim to recruit a sample size of 100 subjects (N1=50, N2=50).

B. Total Number of Subjects If Multicenter Study

Not applicable since this is not a multicenter study.

C. Require Number of Subjects to Complete Research

Total number of subjects required would be 64, however, we shall aim to complete a sample size of 100 subjects.

D. Feasibility of Recruiting

We anticipate that the renal transplant / vascular services may have between 2-4 patients per week, of which we may be able to recruit half of them. Therefore, approximately 100 patients per year may be recruited, and it is feasible to complete the study within the proposed recruitment period.

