6.0 Research Data Protection and Reporting

6.1 Data Management and Confidentiality

A. Aggregated and de-identified data from paper documentation will be input into an SPSS data file, secured on a password-protected computer kept in the P.I.'s locked office and secured by Rutgers-RWJMS access code. Group data will be analyzed using descriptive statistics, t-tests and ANOVA. Results will be evaluated by the P.I. in consort with the co-investigators to determine whether this clinical trial supports a larger study.

B. *Difference in time of supraventricular block with ultrasound compared to without is 20 and 13 min, respectively with a standard of deviation of 10. This gives an S/N ratio of 0.65. The alpha will be set to 0.05, the power will be set to 0.80. This gives a necessary sample size of 33 for each group. 50 in each group will be sufficient.*

C. **Separation of identifiers will be used for each patient. Data will be stored on a secure cloud.**

D. Data entry will be handled by the PI. 10% of the flow sheets will be reentered by a second clerk, [name], who is a member of the research team and the entries compared for accuracy. If there is more than a 1% difference in data entry, the data will be corrected and the test repeated with another 10 percent of the remaining flow sheets. This process will be repeated until there is a less than 1% disparity between the two data entry processes.

E. All data will be gathered using the same data form (Appendix A). Flow sheets of data will be kept in the P.I.'s locked office. Subjects will be identified by a study number and a copy of the data flow sheet given to the data entry clerk. Data analysis of the confidential data set will be performed by the fellows.

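### Operator is named neither in the randomization nor in the analysis; recording it and fitting it in the onset ANOVA is a cheap gain in precision, not a repair of bias

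*Protocol*

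**What the plan says.** - **Allocation.** Protocol 1.3: "After consenting to the study, the patient will be randomly assigned to one of two groups, standard or test treatment". Protocol 4.3: "Subjects will be randomized into 2 treatment groups", with 50 in each. Neither section mentions blocking, stratification or operator.
- **Operators.** Protocol 2.1 uses the plural twice: "All licensed physicians involved with the study will be competent in the administration of ultrasound-guided supraclavicular blocks" and "All investigators are staff MD in the anesthesia department accustomed to the performance of the supraclavicular block". It does not say how many of them place blocks.
- **Outcome.** Protocol 1.6 B: "Dependent variable would be success of the block as measured objectively by speed of onset".
- **Analysis.** Protocol 6.1 A: "Group data will be analyzed using descriptive statistics, t-tests and ANOVA". No factor or covariate is named, and neither method is tied to onset time. Sections 1.5 and 6.1 B size the trial as an unadjusted comparison of two independent samples.
- **SAP.** Sections 7.3 (randomization), 9.3 (covariates) and 11.1 (primary analysis) are unfilled template guidance and name no factor for this trial. The guidance in 9.3 does ask that stratification variables be adjusted for in the primary analysis.

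**The concern.** The protocol expects faster onset because the stimulator may improve where the block is placed relative to the nerve (1.6 B). Placement is done by hand, so the person doing it is an obvious source of variation in onset. If operators differ and the model ignores them, that spread widens the standard error of the treatment difference.

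Precision is at stake, and so is the ability to answer a simple question afterwards: did one arm have more blocks from the faster operators? If the operator is not recorded, that question stays open. The data form (Appendix A) is not among the documents, so it cannot be seen whether it already has an operator field.

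**Working it through.** **Inputs.** From the protocol: difference 20 − 13 = 7 min (1.5, 6.1 B), SD 10, alpha 0.05 and power 0.80 (6.1 B), 50 per arm (4.3, 4.5). Not in the documents, so assumed: 5 operators, and a share r of onset variance lying between operators of 5, 10, 20 or 30%.

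**1. The plan's own figure.** n per arm = 2(1.96 + 0.8416)² × 10² / 7² = 32.04, rounded up to 33, as in 6.1 B. The t-test version gives 33.02, hence 34 as in 1.5. The test is therefore two-sided and unadjusted. Power at 50 per arm: 7 / (10√(2/50)) − 1.96 = 3.5 − 1.96 = 1.54, or 93.8%.

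**2. Gain in principle.** With operator fitted and balanced across arms, the residual SD is 10√(1 − r), equivalent to 1/(1 − r) times the patients.

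| r | residual SD | n per arm for 7 min | power at 50 per arm, 7 min | difference detectable with 80% power, 50 per arm |
|---|---|---|---|---|
| 0 | 10.00 | 33 | 93.8% | 5.60 min |
| 5% | 9.75 | 31 | 94.9% | 5.46 min |
| 10% | 9.49 | 29 | 95.8% | 5.32 min |
| 20% | 8.94 | 26 | 97.5% | 5.01 min |
| 30% | 8.37 | 23 | 98.7% | 4.69 min |

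**3. Simulation, separating the model term from the randomization.** Setting: 100 patients, 5 operators, total SD 10. A range is given where repeat runs differed by more than rounding.

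| Power, % (r = 5 / 10 / 20 / 30%) | 7 min | 5 min |
|---|---|---|
| Plain randomization, t-test | 93 / 93 / 94 / 95 | 70 / 70–72 / 71–72 / 73 |
| Plain randomization, operator fitted | 93 / 94–95 / 96–97 / 98 | 70 / 72 / 77 / 83 |
| Randomized within operator, operator fitted | 94–95 / 95 / 97 / 98 | 71 / 73–75 / 78–79 / 84 |

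The t-test row rises slightly with r because only five operators are drawn: the expected variance in the sample is about 100(1 − r/5), which is 94 at r = 30%. Most of the gain comes from the model term.

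**4. Chance imbalance.** The unadjusted standard error is 10√(2/50) = 2.0 min. At r = 20% with 4–10 operators, uneven allocation of operators shifts the arm difference with an SD of about 0.8 min, and by more than 1 min in about 17–21% of trials. That is 0.64 of the 4.0 units of variance (0.8² against 2.0²). It is already inside the standard error, and simulated type I error of the t-test stays near 5%.

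**5. Cost if operators do not differ.** Under plain randomization, fitting K operators leaves about 1 − (K − 1)/99 of the information: 96% for K = 5. For 7 min, 3.5 × √0.96 = 3.43, so power is about 92.9% instead of 93.8%, a loss of about 1 point. For 5 min the loss is about 2 points. With 8 operators 93% of the information remains, and the losses are about 2 and 3 points. Pooling low-volume operators limits this.

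**6. Stratifying without adjusting.** If randomization is within operator but the analysis is a plain t-test, simulated type I error falls to about 3–4% at shares of 20–30%, so the test is conservative.

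**The case against.** The strongest reply is that precision is not this trial's problem. It enrols 50 per arm against the 33 or 34 it calculates, and power for 7 min is already about 93%. That stands: at the planned effect the gain is a few points at most. It is larger for a smaller true effect, or if the trial closes near the 64 subjects that 4.5 C treats as sufficient. At 32 per arm, unadjusted power is about 79%, and about 83, 87 and 91% with operator shares of 10, 20 and 30% removed.

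The size of the gain is also assumed. One site, one needle type, one volume and staff used to the block all point towards similar operators, and at a 5% share the model term alone gains nothing measurable. Several operators is itself an inference: 4.11 speaks of the block-service anesthesiologist in the singular. That a t-test would be used for onset is likewise only the natural reading for two arms. Finally, onset is checked every 5 minutes and the checks stop at 20 minutes, which is the assumed control mean, so power figures for a continuous normal outcome carry over only roughly. All of this limits the claim to a range.

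A reader might go further and infer that plain randomization leaves the comparison biased or invalid, or that 4.3 must be rewritten to stratify. The documents support neither. Imbalance here is random and is covered by the standard error. Assignment follows consent, and nothing shows that the operator is known by then. At 1–2 recruits a week (half of the 2–4 cases in 4.5 D), small strata in an open procedure would make the next allocation easier to guess.

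**Conclusion.** The point holds as a low-cost improvement in precision. The plan implies more than one operator and names none in allocation or analysis, so any between-operator spread goes into the error term. Simple randomization with an unadjusted comparison remains valid.

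With 5 operators, SD 10 and 50 per arm, the operator term adds between nothing and about 3–4 points of power at 7 min, and between nothing and about 10 points at 5 min, over shares of 5–30%. Randomizing within operator adds under 1 point at 7 min and about 1–3 at 5 min. The direction is secure if operators differ at all appreciably; the size depends on an operator count and variance share that the documents do not give.

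**What to change.** 1. Record the operator of each block on the data form, if it is not already there.
2. In 6.1 A, and in SAP 9.3 and 11.1 when they are written, specify the onset comparison as an ANOVA with treatment and operator. State before the data are seen the rule for pooling low-volume operators into one level.
3. Optional: randomize within operator, only where the operator is known before assignment and the sequence can be concealed (permuted blocks of varying size, list held outside the block team). If this is done, operator must be in the model.

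Steps 1 and 2 cost one data field, one factor in a method the plan already names, and a few degrees of freedom. If operators turn out not to differ, the price with 5 operators is about 1 point of power at the planned effect. No patients or procedures are added.

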4.4 Secondary Subjects

N/A

4.5 Number of Subjects

A. Total Number of Subjects

Locally, we shall aim to recruit a sample size of 100 subjects (N1=50, N2=50).

B. Total Number of Subjects If Multicenter Study

Not applicable since this is not a multicenter study.

C. Require Number of Subjects to Complete Research

Total number of subjects required would be 64, however, we shall aim to complete a sample size of 100 subjects.

D. Feasibility of Recruiting

We anticipate that the renal transplant / vascular services may have between 2-4 patients per week, of which we may be able to recruit half of them. Therefore, approximately 100 patients per year may be recruited, and it is feasible to complete the study within the proposed recruitment period.

4.6 Consent Procedures

A. Consent

▪ **Documenting Consent**

We will document informed consent in writing.

▪ **Waiver of Documentation Of Consent**

We will document informed consent in writing.

▪ **Waiver or Alteration of Consent Process**

(i) **Waiver or Alteration Details**

N/A

(ii) Destruction of Identifiers

N/A

(iii) Use of Deception/Concealment

N/A

B. Consent Process

■ Location of Consent Process

The consent process will take place at the patient's bedside in the holding area or the area where the block will be performed, while the patient still has capacity for consent. Usually it will take place at the same time as the consent for the anesthetic and the supraclavicular nerve block.

■ Ongoing Consent

The patient's ongoing consent is implied as long as the patient remains cooperative during the performance of the supraclavicular nerve block. There is no ongoing intervention requiring consent after the block is placed.

■ Individual Roles for Researchers Involved in Consent

1. Consent Discussion Duration

The consent process and discussion will take place within approximately 30 mins after the patient has consented to the anesthetic and the supraclavicular nerve block. It will last approximately 15 mins.

2. Coercion or Undue Influence

The patient will be of capacity to consent. The patient will be assured that an appropriate anesthetic will be performed regardless of the method used to achieve supraclavicular nerve block. Since every patient will be under the care of an attending anesthesiologist, anesthesia will be ensured to be adequate even in the case that onset, duration, or adequacy of the nerve block is inadequate.

Subjects can be removed from the study immediately any time during or after the intervention or the performance of the supraclavicular nerve block if they express desire to revoke consent or be removed from the study.

3. Subject Understanding

The subject will have a thorough discussion with the anesthesiologist and the recruiter and all questions shall be explained during the consent process.

